9.1 Study design

This study has a cohort design.

Cohorts of first-time users of either rivaroxaban or standard of care will be identified using the date of first dispensing (index date) of the respective drug (index drug).

A patient will be considered eligible to enter the study cohort as a first-time user of rivaroxaban or a first-time user of “standard of care” when he or she has a first dispensing of the drug recorded during the enrolment period. In the Netherlands, for VTE prevention, DVT/PE treatment and SPAF, standard of care is treatment with a vitamin K antagonist (acenocoumarol or phenprocoumon), and for the secondary prevention of ACS, standard of care is antiplatelet drug(s) such as low-dose acetylsalicylic acid, clopidogrel, dipyridamole, prasugrel, ticlopidine and ticagrelor.

Patients who qualify as members of both cohorts on the same day, will be excluded. First-time users who have any record of being prescribed the other study drug prior to the enrolment period can only join their index drug cohort; these will be categorized as non-naïve, see below (i.e. patients with a previous dispensing of rivaroxaban can only join the standard of care cohort and those with a past dispensing for standard of care can only join the rivaroxaban cohort).

Patients who are first-time users of both rivaroxaban and comparison study drugs during the enrolment period will be assigned to a cohort based on first dispensing, with the date of this dispensing being the index date.

Many patients with ACS have a history of ischaemic heart disease for which platelet inhibition is standard treatment, and thus exclusion of patients with prior use of platelet inhibitors risks excluding a majority of typical ACS patients. Therefore, in patients treated for ACS, those who have been using a vitamin K antagonist or another oral anticoagulant-before the index date will be excluded but those who have been using one or more platelet inhibitors will remain eligible to enter the study.

Standard of care for ACS patients is combination therapy, and as such cohort assignment will be based on first use of rivaroxaban (in combination with aspirin or clopidogrel, or multi-antiplatelet therapy), or use of aspirin and clopidogrel and/or other antiplatelet medications.

Study subjects for DVT/PE treatment and SPAF will be categorized as naïve or non-naïve patients according to their previous use of any comparator drugs (Figure 1). Naïve patients will be those without a previous dispensing of the comparator drug recorded before the index date. Non-naïve patients will be those with one or more dispensing of the comparator drug recorded before the index date. Non-naïve patients will be further subdivided into recent switchers (patients exposed to the other study drug in the 6 months prior to the index date) and distant switchers (patients exposed to the other study drug more than 6 months prior to the index date).

[figure not shown]

Figure 1. Subdivision of study cohorts for DVT/PE treatment and SPAF.

Data collected for comparison of cohorts is described in [Section 9.3](#)

Strengths of the study pertaining to the research question include:

- It uses observational data from routine clinical practice with no selection and no possibility to influence prescribing behaviour.
- PHARMO is a well-validated resource for pharmacoepidemiology research (see [Section 9.2](#)).

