- The prevention of venous thromboembolism (VTE) in adult patients undergoing elective hip or knee replacement surgery (recommended dose: 10 mg rivaroxaban od for 35 days following hip replacement surgery and 14 days following knee replacement surgery).
- Co-administered with acetylsalicylic acid (ASA) alone or with ASA plus clopidogrel or ticlopidine, for the prevention of atherothrombotic events in adult patients after an acute coronary syndrome (ACS) with elevated cardiac biomarkers (recommended dose 2.5 mg bid).

As is the case with other anticoagulants, clinical studies of rivaroxaban have identified haemorrhage as an important safety outcome ([Lassen et al. 2008](#); [Turpie et al. 2009](#)). A post-authorization safety study programme is planned for several European countries. The aim of this document is to summarize the design of a population-based study to characterise new users of rivaroxaban, assess patterns of drug utilization, including adherence to label recommendations, and to assess the risk of bleeding associated with rivaroxaban treatment in comparison with treatment with standard of care, in routine clinical practice in the Netherlands, for DVT/PE treatment, SPAF and ACS. For DVT/PE treatment and SPAF, standard of care is treatment with a vitamin K antagonist (acenocoumarol or phenprocoumon), and for the secondary prevention of ACS, standard of care is antiplatelet drug(s) such as low-dose acetylsalicylic acid, clopidogrel, dipyridamole, prasugrel, ticlopidine and ticagrelor. The standard of care treatments for ACS will require at least dual antiplatelet and be analysed as combination treatment, irrespective of the individual drug combinations used.

8 Research questions and objectives

This post-authorization study was designed to assess patient characteristics and patterns of drug utilization and to quantify outcomes related to safety and effectiveness in new users of rivaroxaban compared with new users of standard of care.

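### ACS cohorts: patients already on dual antiplatelet therapy can enter a comparator described as new users, and the rules for its entry and index date are not reconciled

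*Protocol*

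**What the plan says.** Section 8 of the protocol describes the comparison as "new users of rivaroxaban compared with new users of standard of care". Section 9.1 takes the index date from the first dispensing of the index drug and then gives a general entry rule: "First-time users who have any record of being prescribed the other study drug prior to the enrolment period can only join their index drug cohort". A bracketed explanation adds that "those with a past dispensing for standard of care can only join the rivaroxaban cohort". Neither sentence is limited by indication. The rule labels such patients non-naïve and points forward to the definition of that term.

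The same section says that "for the secondary prevention of ACS, standard of care is antiplatelet drug(s) such as low-dose acetylsalicylic acid, clopidogrel, dipyridamole, prasugrel, ticlopidine and ticagrelor". Section 7 adds that the ACS comparator must be at least dual antiplatelet therapy and is analysed as a combination.

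Two ACS paragraphs follow in 9.1. The first gives a reason, that "exclusion of patients with prior use of platelet inhibitors risks excluding a majority of typical ACS patients", and concludes that "those who have been using one or more platelet inhibitors will remain eligible to enter the study". The second says that "cohort assignment will be based on first use of rivaroxaban" together with antiplatelet treatment. For the comparator it refers to use of aspirin and clopidogrel and/or other antiplatelets, without repeating the word *first*.

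The subdivision by earlier treatment is then restricted: "Study subjects for DVT/PE treatment and SPAF will be categorized as naïve or non-naïve patients".

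**The concern.** ACS is one of the three populations in which the primary bleeding outcomes are compared (Section 8.1.2 and the objectives at the front of the protocol). A new-user comparison needs each patient to start the treatment under study at time zero. If the comparator admits patients who have already been on the same dual therapy for some time, those who bled early on it and stopped are under-represented. The rivaroxaban cohort, by contrast, is observed from its first dispensing of rivaroxaban.

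The index date also governs much else: the exclusion for earlier oral anticoagulant use (9.1), the year of prior registration (9.2), the hospital-diagnosis window from 4 weeks before to 7 days after index and the look-back for co-medication (9.3.1), and the start of follow-up (9.7.2). If two analysts could date the same comparator patient differently, all of these shift.

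**Working it through.** The protocol gives no figure for this point. Its only size calculation (Section 9.5) concerns vitamin K antagonist comparators. It reproduces if a two-sided alpha of 0.05 is assumed, since none is stated. With a rate ratio of 1.5, 1:4 allocation and 80% power, the events needed are (1.960 + 0.842)² / (0.2 × 0.8 × (ln 1.5)²) = 7.85 / (0.16 × 0.1644) ≈ 298.4, rounded up to 299. At 5 per 1000 person-years that is 299 / 0.005 = 59,800 person-years, against 12,000 + 48,000 = 60,000 stated. It has no ACS component and neither supports nor weakens the point.

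The check is therefore textual. Four ACS patients can be passed through the rules.

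1. *No earlier antiplatelet; starts two antiplatelets after the ACS.* Every rule agrees: comparator cohort, new user, index date at the start.
2. *Long-term aspirin; adds clopidogrel after the ACS.* Taken literally, the general rule bars this patient from the comparator, because aspirin is ACS standard of care. The ACS exception keeps the patient eligible. He or she is a new user of the dual combination, but not of the first drug in it. The text does not say whether the index date is an aspirin dispensing or the clopidogrel dispensing that makes the therapy dual.
3. *Already on aspirin and clopidogrel; continues after the ACS.* The exception covers users of one or more platelet inhibitors, so the patient is eligible. The assignment sentence asks the comparator only for use, so the patient qualifies. Nothing is started, so this is not a new user in the sense of Section 8, and the index date can only be a refill.
4. *Already on aspirin and clopidogrel; adds rivaroxaban.* The patient enters the rivaroxaban cohort on the day of first use, with a clear time zero.

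Patients 3 and 4 show the asymmetry. Both have the same antiplatelet history, but one enters at a treatment start and the other at an arbitrary point in ongoing treatment.

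The analysis does not reliably separate these patients. The naïve/non-naïve strata cover DVT/PE treatment and SPAF only. Section 9.7.2 offers adjustment for co-medication only if numbers and data allow.

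**The case against.** The strongest reply is that the general rule was never meant for ACS. It refers the reader to the non-naïve category, which the protocol then confines to DVT/PE and SPAF. The ACS paragraph comes later, is specific to the indication, and gives its reason. This largely stands. A reader might infer that the ACS comparator is to be stripped of everyone with earlier antiplatelet use, but that is the outcome the exception was written to prevent. What remains is that the exception says only that such patients may enter the study. It names no cohort and does not say that it displaces the general rule.

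A second reply is that an earlier aspirin user who starts dual therapy is a new user of the combination, and that the opening of 9.1 applies first-time use to both cohorts. The first part is right, so it would be too strong to say that the comparator as a whole is not a new-user cohort. But the protocol nowhere requires first use of the combination, and its wording admits patient 3.

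A third reply is that dating a combination can be left to the SAP. The programming detail can. The event that brings a patient into the cohort is design, and here the stated definition (first dispensing of a drug) does not fit the stated comparator (at least two drugs).

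Finally, earlier antiplatelet users can be in both ACS cohorts, and rivaroxaban users in ACS also take antiplatelets. Tolerance of earlier antiplatelets is therefore not peculiar to comparators. This stands, and it is one reason why no direction of bias can be claimed.

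**Conclusion.** The point holds as an inconsistency in the ACS entry rules. The general rule is not expressly lifted for ACS. Under the exception that evidently replaces it, the rivaroxaban cohort starts at first use while the comparator can include patients already on dual therapy. The comparator's index date is not fixed by a definition that suits a combination, and no planned stratum separates earlier users in ACS.

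Prevalent-user bias in the ACS bleeding and MI contrasts is possible. Its size and direction cannot be computed from the document, which gives neither the number of ACS patients nor the share already on dual therapy. The remark about losing most typical ACS patients might be read as showing that over half of the comparator is at stake. It is a qualitative reason about ACS patients in general and supports no such figure. Nor does the document support a claim that the bias runs in opposite directions under different readings.

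The conclusion assumes that the ACS exception governs and that the comparator wording is applied as written. It concerns ACS-specific rates and ratios, not those for DVT/PE treatment or SPAF.

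**What to change.** In Section 9.1:

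- State that the rule sending past standard-of-care users to the rivaroxaban cohort applies to DVT/PE treatment and SPAF only, and that in ACS earlier antiplatelet users may enter either cohort.
- Define ACS entry and index date in the same way in both cohorts: the first dispensing in the enrolment period that completes the cohort-defining combination (rivaroxaban with antiplatelet therapy, or at least dual antiplatelet therapy). Patients already on that combination do not count as new users.
- Stratify or adjust the ACS comparison by antiplatelet use in the year before index. This is still needed after the second change, because a rivaroxaban starter may already be on dual therapy while a comparator entrant may not.

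No new data are required. Section 9.3.1 already lists antiplatelet use in the year before index, and Section 9.2 requires a year of prior registration in the dispensing database. The cost is the loss of some comparators already on dual therapy, a few sentences of protocol text and minor programming.

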9.2 Setting

Study drug users will be selected from the outpatient pharmacy database. This database records all outpatient dispensings from primary and secondary care in a well-defined geographic area. All study drug users living in this area will be captured in the database. All patients aged 2 years and above who have been registered in the database for at least 1 year before the index date will be included. A sub-population will be defined of patients for whom GP recorded information is also available.

The enrolment period will start on December 10, 2011 (the day after rivaroxaban received first marketing authorization in the Netherlands for the ‘treatment of DVT and long-term secondary prevention of recurrent DVT and PE’). End of enrolment will be 31 December 2017 and end of follow-up will be 31 December 2018. Interim reports will be provided for data collected 2 and 4 years after the date that rivaroxaban receives reimbursement approval for DVT treatment (see [Section 6](#) for detailed milestones). The characteristics of the two study cohorts in the first year and subsequent years of the enrolment period will be compared.

The drug utilization analysis ([Section 8.1.1](#)) will be performed in the sub-population captured by both the outpatient pharmacy database and the GP database, in order to enrich the data for the assignment of indication of use.

The Adverse Outcomes analysis (Sections [8.1.2](#) and [8.2](#)) will be performed in the full rivaroxaban cohort (outpatient pharmacy database with outcomes available from Medical Register), using the dosing as a proxy for the indication when this information is not available, and in the subcohort of comparator drug users captured by both the outpatient pharmacy database and the GP database.

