Number	Date	Section of study protocol	Amendment	Reason
6	Jan 2015	9.3.2.1 9.7.2 9.7.2.1	Addition to section on bleeding definition Addition to section on renal failure definition Addition of section to handle missing data	Response to PRAC review
5	Nov 2014	8.2 9.3.1 9.7.1 9.7.2.1 Annex 3	Additional variables for patient characterisation and analyses thereof; strengthened analyses of renal impairment. Table 12, ICD codes related to renal impairment added	Response to PRAC review
4	May 2014	General	Extension of study timelines. Comparator updated for acute coronary syndromes. Added secondary safety outcome: "other bleeding" Transfer to EMA protocol template. Label wording updated. Current protocol is V5.0.	PRAC request
3	Mar 2012		Inclusion of additional indication, treatment of pulmonary embolism. V4.0 of protocol.	Label expansion
2	Dec 2011		Inclusion of additional indication, acute coronary syndrome. V3.0 of protocol submitted with EU RMP V	Label expansion

			7.1	
1	Apr 2011		Inclusion of additional indication, stroke prevention in atrial fibrillation. V2.0 of protocol submitted with EU RMP V 6.1.	Label expansion

6 Milestones

Table 2: Milestones

Milestone	Planned date
Start of data collection (Marketing Authorization granted for DVT treatment)	Q1 2012
Interim report 1 2 years drug utilization data and crude incidences for primary safety outcomes	Q4 2015
Interim report 2 4 years drug utilization data and crude incidences for primary safety outcomes	Q4 2017
End of data collection	Q4 2018
Final data availability	Q4 2019
Progress reports	Annual in November 2014–19
Final report of study results with full outcomes analysis	Q4 2020
Registration in the EU PAS register	Study to be registered after PRAC approval

7 Rationale and background

Rivaroxaban, a direct Factor Xa inhibitor, is licensed for multiple indications:

- The treatment of deep vein thrombosis (DVT) or pulmonary embolism (PE), and prevention of recurrent DVT and PE in adult patients (DVT/PE treatment) (15 mg rivaroxaban twice daily [bid] for 3 weeks, then 15 mg or 20 mg once daily [od]).
- The prevention of stroke and systemic embolism in adult patients with non-valvular atrial fibrillation (stroke prevention in atrial fibrillation [SPAF]) with one or more risk factors, such as congestive heart failure, hypertension, age \geq 75 years, diabetes mellitus, prior stroke or transient ischaemic attack (20 mg rivaroxaban od).

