9.3 Variables

9.3.1 Patient characteristics and drug utilization

Descriptive variables of drug utilization will be presented only for the subpopulation captured by both the outpatient pharmacy database and the GP database, as only in this subpopulation sufficient information for the assignment of the indication of use is available. The following characteristics, including risk factors/potential confounders for the outcomes under study, will be presented for comparison between the two cohorts:

- age and sex distribution at index date 
- dose of index drug at index date (not available for vitamin K antagonists as dosing is determined in anticoagulation clinics) 

- dispensed amount (can be used to estimate duration of treatment) ✓
- where available based on hospital discharge diagnosis or from available GP notes, diagnosis associated with the prescribing of the index drug (where not available, dose and duration of index drug will be used as a proxy for the associated diagnosis among rivaroxaban users). Hospital discharge diagnoses and procedures will be identified within 4 weeks before until 7 days after the index date and GP diagnosed will be identified during the index month or in the month before the index date.
- proportion of patients defined as naïve, non-naïve, recent switchers and distant switchers ✓
- number of pregnant women at index date (if communicated by midwife or gynaecologist) ✓
- number of pregnancies after index date (if communicated by midwife or gynaecologist) ✓
- type of other anticoagulant use before the index date among the non-naïve group ✓
- use of specific prescribed medications both in the year before the index date and following the index date, confirming the ACS indication: antiplatelet drugs (low-dose acetylsalicylic acid, clopidogrel, dipyridamole, prasugrel, ticlopidine and ticagrelor); ✓

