9.7.2 Safety and effectiveness outcomes

The two cohorts (of first-time users of rivaroxaban and first-time users of standard of care) will be followed up from the index date until 12 months after the end of the enrolment period for potential outcomes (safety and effectiveness). For each outcome, the first hospitalization for that outcome during the follow-up period will be identified. A separate follow-up will be performed for each of the outcomes.

For all outcomes (for DVT/PE treatment, SPAF and ACS), crude incidence rates will be estimated in both cohorts, using an as-treated approach. In this, person–time will be categorized into current, recent, past and non use. Current use will refer to person–time up to 7 days after the end of supply of the index drug, recent use will refer to person–time up to 90 days after the end of current use, past use will include all person–time contribution after the end of recent use up to 1 year after the end of current use, non-use will include all remaining time person–time contribution after past-use until end of follow-up.

Age- and sex-adjusted rate ratios with 95% CIs will be estimated for each of the three adverse outcomes comparing rivaroxaban with standard of care using Poisson regression analysis. Where numbers and data permit, adjustment will be made for relevant co-medication (described in the drug utilization section), indication and previous hospitalization for bleeding.

As a general strategy, no data imputation strategies will be applied to supplement missing data. The requirement for inclusion is complete data for critical variables such as exposure to rivaroxaban or standard of care and hospitalizations for bleedings or any other outcome event; otherwise this individual is not eligible to be a member of the study population. However, missing values may occur for potential confounder or effect modifying variables. In this case, individuals with missing values will be kept in the analysis and a separate category will be created for missing values of that variable. In sub-analyses to evaluate confounding or effect modification by variables with a large proportion of missing values, the evaluation will be considered to be conducted on the subset with complete data for the variable of interest.

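### The SPAF outcome comparison is not restricted to non-valvular atrial fibrillation, so valve patients can enter mainly the vitamin K antagonist cohort and may bias the rate ratio

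*Protocol*

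**What the plan says.** Section 7 gives the SPAF indication as "The prevention of stroke and systemic embolism in adult patients with non-valvular atrial fibrillation", with one or more risk factors.

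Entry is wider. Section 9.2 takes "All patients aged 2 years and above who have been registered in the database for at least 1 year before the index date". Section 9.1 makes first-time users of acenocoumarol or phenprocoumon the SPAF comparator and sets no condition on valve disease. It does set an indication-specific exclusion for ACS, where earlier oral anticoagulant users are removed.

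Indication is assigned under 9.3.1: "Hospital discharge diagnoses and procedures will be identified within 4 weeks before until 7 days after the index date". GP diagnoses are taken from the index month or the month before. For the outcome analysis, 9.2 uses the full rivaroxaban cohort, "using the dosing as a proxy for the indication when this information is not available", against only those comparator users who also have GP data.

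The analysis in 9.7.2 is: "Age- and sex-adjusted rate ratios with 95% CIs will be estimated for each of the three adverse outcomes". Co-medication, indication and earlier hospitalization for bleeding are added where numbers and data permit. Valve disease is not among the characteristics in 9.3.1, the adjustment variables in 9.7.2 or the limitations in 9.9.

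**The concern.** The entry rule is the same for both cohorts, but its effect need not be. Because the SPAF indication quoted in section 7 covers non-valvular fibrillation only, patients with mitral stenosis or a prosthetic valve who start an anticoagulant would be expected mainly among VKA users. If they are counted as SPAF, the comparator contains a kind of patient that is scarce on the rivaroxaban side.

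Nothing planned separates them. A valve diagnosis or operation recorded well before the index date lies outside the window in 9.3.1. A dose proxy cannot show valve status. The indication term in the model distinguishes SPAF from DVT/PE treatment and ACS, not valvular from non-valvular fibrillation.

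At stake are the SPAF rate ratios for the three primary bleeding outcomes and the secondary outcome comparisons in SPAF. If valve patients bleed more than other VKA users, rivaroxaban would look safer than it is in the population of section 7, which is the unfavourable direction for a safety study. If they bleed less, the error runs the other way.

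**Working it through.** **1. The plan's own figure.** Section 9.5 gives 5 haemorrhagic strokes per 1,000 person-years on VKA, 12,000 rivaroxaban and 48,000 VKA patient-years, a 50% increase to be excluded, and 80% power. Alpha is not stated. I take it as two-sided 0.05, in line with the 95% intervals in 9.7.2.

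- Expected events at a true rate ratio of 1: 12,000 × 0.005 = 60 and 48,000 × 0.005 = 240.
- SE of the log rate ratio: √(1/60 + 1/240) = 0.144.
- Power: Φ(ln 1.5 / 0.144 − 1.96) = 80.2%.

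The study size reproduces, and the present point leaves it untouched. The issue is bias, not precision.

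**2. Bias from valve patients in the comparator.** Let f be the share of SPAF comparator person-time from valve patients, and k their event rate relative to the other comparator patients. With no such patients on rivaroxaban, and none of the difference absorbed by the age and sex adjustment,

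observed RR = true RR / (1 + f(k − 1)).

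The documents give neither f nor k. The ranges below are assumptions. With a true RR of 1.00 the observed RR is:

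| f | k = 0.8 | k = 1.5 | k = 2.0 |
|---|---|---|---|
| 2% | 1.00 | 0.99 | 0.98 |
| 5% | 1.01 | 0.98 | 0.95 |
| 10% | 1.02 | 0.95 | 0.91 |
| 20% | 1.04 | 0.91 | 0.83 |

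Example: f = 10%, k = 1.5 gives 1 / (1 + 0.10 × 0.5) = 1/1.05 = 0.95.

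If a share g of rivaroxaban SPAF person-time is also valvular, with the same k, the numerator is multiplied by 1 + g(k − 1). The bias shrinks and vanishes at g = f, so the table shows the most asymmetric case.

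**3. Effect on the stated aim of excluding a 50% increase.** Suppose the true RR is 1.5. Rivaroxaban events are then 60 × 1.5 = 90 and comparator events 240 × (1 + f(k − 1)). The chance of wrongly excluding 1.5 is Φ(ln(1 + f(k − 1)) / SE − 1.96), nominally 0.025. For f = 10%, k = 1.5: comparator events 252, SE = √(1/90 + 1/252) = 0.123, and Φ(0.0488/0.123 − 1.96) = 0.059.

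| f | k = 0.8 | k = 1.5 | k = 2.0 |
|---|---|---|---|
| 5% | 0.021 | 0.039 | 0.059 |
| 10% | 0.017 | 0.059 | 0.119 |
| 20% | 0.011 | 0.119 | 0.326 |

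This treats all the person-years in 9.5 as SPAF, which the protocol does not say. It shows scale only.

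**4. Cost of restricting.** If 2%, 5%, 10% or 20% of the 48,000 VKA patient-years are removed, the formula in step 1 gives power of 80.1%, 79.8%, 79.3% or 78.3%. For 10%: 43,200 × 0.005 = 216 events, SE = √(1/60 + 1/216) = 0.146, power 79.3%.

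**The case against.** Several points on the other side have weight.

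- *New-user rule.* Section 9.1 requires a first dispensing in the enrolment period. A patient on a VKA since a valve operation years ago should mostly not enter, and one starting around a new operation falls inside the 9.3.1 window, which covers procedures. This stands and argues for a small f. What remains are new VKA starters with older valve disease, for example known mitral stenosis with newly diagnosed fibrillation.
- *SPAF already means non-valvular, and there is an "other" stratum.* True as a label. But no rule sends a patient with fibrillation and an older valve record to that stratum, and the assignment window would not show the record. Annex 3 has no code list for any indication, so the lack of valve codes there is not itself a fault. Such lists are commonly left to the statistical analysis plan.
- *History is read further back elsewhere.* Section 9.7.2.1 uses renal diagnoses at any time before index. This shows that a long look-back is feasible, not that one is planned for valve disease.
- *Wide entry is deliberate.* Section 7 aims to "assess patterns of drug utilization, including adherence to label recommendations", and 9.1 lists as a strength: "It uses observational data from routine clinical practice with no selection". That justifies wide entry for the utilization description. It does not require it for the SPAF rate ratio.

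A reader might infer that the age limit of 2 years itself distorts the comparison. The documents do not support that: the limit is common to both cohorts, age is in the model, and children in a SPAF stratum would be very few.

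**Conclusion.** The point holds in limited form. Followed as written, the protocol lets new VKA users with valvular fibrillation into the SPAF comparator, and no planned adjustment separates them. The SPAF rate ratio is therefore potentially biased. Under the assumed ranges (share 2-20%, relative event rate 0.8-2.0, none on rivaroxaban) a true ratio of 1.0 appears as about 0.83-1.04. At shares of 2-5% the shift is small, at most from 1.00 to 0.95. It becomes material at about 10% or more with a clearly different event rate.

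A reader might go further and conclude that the SPAF rates are not comparable, or that rivaroxaban is necessarily favoured. Neither is shown. The protocol gives no valve share and no event rate for these patients, does not confine rivaroxaban users to the label, and through its first-dispensing rule removes most long-standing valve patients. That they are found mainly among VKA users is an expectation drawn from the indication wording in section 7. The study size in 9.5 is unaffected.

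**What to change.** 1. For the SPAF outcome analyses (8.1.2 and 8.2), exclude from both cohorts patients with a hospital discharge record of mitral stenosis or a prosthetic heart valve at any time before index. State the codes, in ICD-10 as well once that transition (9.4) takes effect. Use the Medical Register, which 9.4 describes as fully linked to the outpatient pharmacy database, so that the main restriction rests on the same source in both cohorts.
2. Do not add GP valve records to that main restriction. Comparators all have GP data and many rivaroxaban users may not, so valve disease would be found more often in one cohort. Instead, repeat the analysis in the GP-linked subset of both cohorts with GP valve records added.
3. Name residual, unrecorded valve disease as a limitation in 9.9.
4. As a minor alignment with section 7, restrict the comparative outcome analyses to adults. Keep the wide entry, including valvular fibrillation and ages from 2 years, for the drug-utilization description, where it shows use outside the label.

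The cost is a short code list, some wording and a small loss of VKA person-time: power falls from 80.2% to 79.3% if 10% of VKA patient-years are removed.
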